Title: Adductor Canal Mid-thigh and Adductor Canal Distal Thigh: Is Cutaneous Sensory Blockade Similar Among Block Techniques?

NCT02788019

Document Date: 05/06/2016 (Date IRB officially approved)

**The University of Texas Southwestern Medical Center at Dallas
Institutional Review Board**

Protocol (for Investigator Initiated Studies)

Title: Adductor Canal Mid-thigh and Adductor Canal Distal Thigh: Is Cutaneous Sensory Blockade Similar Among Block Techniques?

Principal Investigator: [name].

Co-Investigators:

[name].

[name].

[name].

[name].

[name].

[name]

Funding Source: UT Southwestern Department of Anesthesiology and Pain Management.

1. Introduction and Purpose:

The adductor canal block (ACB), or the “sub-sartorial mid-thigh” or “distal thigh saphenous block”, are relatively new approaches in which local anesthetic is deposited within an aponeurotic tunnel in the middle-third of thigh containing multiple nerves.¹⁻⁵ ACB is predominately a blockade of multiple sensory nerves block with limited motor involvement. The block is utilized for knee surgery and for medial blockade of the leg (i.e., at or below the knee).⁶⁻⁹

The primary nerves located in this area are the saphenous nerve and a single efferent motor nerve, which is the distal branch of the femoral nerve that innervates the vastus medialis of the quadriceps muscle. In the distal portion of the adductor canal, a sensory branch of the posterior obturator nerve often enters the canal.^{10,11} It is unclear if other nerves are found regularly in this anatomic location though it has been suggested that the medial femoral cutaneous nerve and medial retinacular nerve may be among them.⁹ Debate is ongoing within the regional anesthesia literature regarding anatomy, differences of block technique and their potential effects on block results.¹²⁻¹⁵ While comparisons of block technique have been studied,^{16,17} there are no published studies regarding cutaneous sensation in light of the newly defined block technique parameters, to our knowledge.^{10,12-14,18} We seek to confirm that the areas of sensory blockade are the same or differ following the two different types of adductor canal block in the area that is proximal to the knee. This knowledge can help improve patient analgesia and lower postsurgical opioid consumption for future patients having surgery in this area.

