1. MVIC
2. Post-operative Pain scores, stratify to type of surgery
3. Opioid consumption
4. Block performance time
5. Characterization of cutaneous sensory block area by sensory mapping
6. Patient satisfaction

2. Background:

The adductor canal block is used for surgical anesthesia and/or postoperative pain control for surgeries involving the medial foot, medial ankle or medial leg. Different investigators have described varying techniques in accomplishing the adductor canal block as detailed here:

Manickam (distal thigh adductor canal): “The leg...was externally rotated, the knee slightly flexed. The medial aspect of the thigh was scanned in a transverse axial plane using a high-frequency linear probe prepared in a sterile fashion. The saphenous nerve was identified in a cross-sectional (short axis) view as it runs alongside the femoral artery in the adductor canal deep to the sartorius muscle. The transducer was initially placed on the medial aspect of the distal third of the thigh to identify the femoral artery immediately deep to the sartorius muscle. The transducer was then moved caudally along the long axis of the thigh until the femoral artery was seen “diving” deep and moving away from the anterior muscle plane (sartorius and vastus medialis muscles), toward the posterior aspect of the thigh where it becomes the popliteal artery. This area was identified as the “adductor hiatus,” and the block location was selected 2 to 3 cm proximally to this area, in the distal adductor canal...The nerve was identified as a slightly hyperechoic structure with a round cross-section, in close relationship to the femoral artery, usually slightly superficial to it.”¹

Lund/Jaeger/Machi: mid-thigh adductor canal “A high-frequency linear ultrasound transducer was placed transverse to the longitudinal axis of the extremity at the mid-thigh level at a distance approximately halfway between the iliac spine and the patella. The femoral artery was identified underneath the sartorius muscle with the vein just underneath the artery. At this position, the saphenous nerve was placed lateral to the artery in the adductor canal. A 10cm Tuohy...was inserted, in plane, from the lateral side of the transducer, through the sartorius muscle with the tip placed lateral to the artery.”⁵

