“The midpoint between the anterior superior iliac spine and the cephalad margin of the patella was measured with slight external rotation of the leg at the hip. Using ultrasound at this midpoint, the superficial femoral artery was identified in a short-axis view deep to the sartorius muscle, medial to the rectus femoris muscle and anterior to the adductor longis muscle, with the superficial femoral vein usually posterolateral to the artery. At this position, the ultrasound image of the saphenous nerve or nerve bundle is typically anterolateral to the superficial femoral artery within the adductor canal. The corresponding anatomical positions for each structure are saphenous nerve anterior to the artery, vein lateral to the artery, and sartorius medial to the artery...the final needle tip positioning between the artery and the saphenous nerve. If the saphenous nerve could not be well visualized, the needle tip was placed at 5 o’clock relative to the femoral artery within the adductor canal.”⁸

3. Concise Summary of Project:

This investigation will be a randomized interventional prospective pilot study. Patients undergoing medial foot, medial ankle, or medial leg surgery (n= 68) will be randomized to evaluate two types of adductor canal blocks. Patients will be identified during their orthopedic presurgical clinic visit, anesthesia preoperative clinic visit or Day Surgery Unit (Zale Lipshy Hospital, Clements University Hospital, UTSW Outpatient Surgery Center) for the eligibility. The electronic medical record (Epic) will also be used for prescreening of potential study participants by reviewing the clinic visit daily schedule or operating room schedule. Then patient charts will be reviewed for initial data collection to determine the eligibility of potential subjects with the use of a HIPAA waiver form. Eligible individuals may be introduced to the study in the orthopedic presurgical clinic or the anesthesia preoperative

clinic by staff. Those individuals interested in participation will then be contacted to learn about the study by study personnel.

A discussion of risks, benefits and alternatives will be performed.

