 - Sensory blockade will be assessed over a grid area. The grid will be marked starting with anatomical landmarks at the knee joint: the medial inter-knee-joint point where the tibia meets the femur, the mid medial patella, the mid lateral patella, and along the same line at the semitendinosus tendon and 5cm posterior from that point. Then 5cm intervals will be plotted progressing cephalad to a total of 15 centimeters. This yields 20 grid points.
 - The study will use a 20 point-grid to standardize evaluation of sensory blockade in the anticipated border zone of block distribution. It will take approximately 1-2 minutes to make the grid and perform the testing. This is specifically for research purposes.
 - **Pinprick testing:**
 - The Sensory block for sharp sensations will be assessed by using Pinprick testing. Pinprick testing will be tested on a scale of 0-1, with 1 = normal sharp sensation and 0 = dull change of sensation, using a Neuropen for standardization of force.¹⁹⁻²¹
 - Sensation to the Neuropen will be performed gently across the skin with the end of the device to assess sharp touch. The subject will be asked to determine whether the stimulus feels sharp. The number of grid-points with a change in sensation from baseline will be recorded at 20-minutes and 30-minutes after the block.
 - Mechanical stimulation with pinprick testing is routinely used to test nociception in the bedside neurologic examination. Sharpness can be considered a surrogate for nociception because, whereas sharpness is not necessarily painful, mechanical thresholds for sharpness closely parallel those for pain.²⁶
 - **Maximum Voluntary Isometric Contraction:**
 - The MVIC will be assessed with a handheld dynamometer (Lafayette Instrument Company; Lafayette, Indiana).

- The patient will be in a seated position with the thigh parallel to the floor and the knee at a 90-degree angle with the feet off the floor. The dynamometer is applied to the leg 5 cm above the transmalleolar axis and perpendicular to the tibial crest. The patient is instructed to extend the leg at the knee with sustained maximal force for 5 seconds. This will be repeated 3 times with 30 seconds rest between each movement, and the force will be recorded. MVIC will be assessed at baseline and again at 20 minutes and 30 minutes post block.
 - **Adductor Canal Blockade:**

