Stored electronic data that contains PHI and/or other types of identifiable data will be encrypted and password protected and stored on a secure server. Subject identifiers will not be reused or disclosed to any other person or entity for research unless required by law, for authorized conduct and oversight of the study, or for other IRB-approved research.

All protected health information will be kept in a secure location with limited access.

Following the completion of the analysis and the project, the key to the coding system will be destroyed by shredding the documents so that there is no direct or indirect link to subject identifiers and information.

13. Potential Benefits:

Potential benefits in determining whether the two neurosensory blockade techniques are different include identifying a potential difference in the area of sensory blockade of the thigh, a potential difference in strength as indicated by MVIC, as well as suggesting a potential improvement in analgesia of the thigh and subsequent increase in patient satisfaction, as well as decreased postoperative opioid usage for future patients.

Both neurosensory blockade techniques are very safe, have little or no pain associated with administration, and have the same cost.

14. Biostatistics:

Sample Size Estimation:

There is no prior study to provide basis for a sample size estimation. Thus the study is powered to achieve 70% power with two-sided alpha = 0.05 for testing the equivalence of the two blocking methods. With an equivalence margin of 2 points (two blocking methods will be equivalent if mean score for one blocking method within two points of the other) and assuming a standard deviation of 3 points, the study will have 70% power with n = 34 in each group (total n = 68).

Statistical analyses:

Data will be summarized as mean and standard deviation for continuous variables and frequency and percentages for categorical variables. The equivalence of the two blocking methods will be tested using the two-one-sided-tests (TOST) procedure following Schuirmann (1987).²⁸ Pain scores and opiate consumption will also be analyzed in subgroups according to the location and type of surgery (foot vs. ankle vs. leg) and presence of concurrent sciatic block.

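### The primary grid count is capped 15 cm above the knee with no rule for a numb top row, so equivalence on the grid need not mean equivalence of the blocked area

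*Combined protocol and SAP*

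**What the plan says.** Section 1 sets the question: "We seek to confirm that the areas of sensory blockade are the same or differ following the two different types of adductor canal block", for the region above the knee. It names no upper boundary.

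Sections 3 and 4 define the grid. Five landmarks lie around the knee joint, and from these "Then 5cm intervals will be plotted progressing cephalad to a total of 15 centimeters". Rows at 0, 5, 10 and 15 cm in five columns give the stated 20 points. Each point is scored as normal or changed, and the number changed at 20 and 30 minutes is the primary outcome. Section 4 explains that the grid is placed where the edge of the block is expected. No rule covers a patient whose 15-cm points are changed.

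Section 2 describes the two injection levels. For the mid-thigh block, "The midpoint between the anterior superior iliac spine and the cephalad margin of the patella was measured". For the distal block, the adductor hiatus is located and "the block location was selected 2 to 3 cm proximally to this area, in the distal adductor canal". Neither is given as a distance above the knee.

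Section 14 tests equivalence by TOST: "With an equivalence margin of 2 points", "assuming a standard deviation of 3 points", 34 patients per group and 70% power. Sensory mapping of the blocked area is a separate secondary endpoint, without a described method or extent.

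**The concern.** A count with a ceiling cannot register skin numbed above that ceiling. If numbness passes the top row more often in one arm, that arm loses more points. On the injection levels described, that is more likely the mid-thigh arm. The difference in means then shrinks. So does the SD, because patients pile up at the maximum.

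In a superiority trial both effects of a ceiling would be a nuisance. Under TOST both work towards the positive conclusion. The trial could call the areas equivalent when the part of the thigh where they differ was not tested. Section 14 also allows stopping at half enrolment if the two techniques look sufficiently alike, so a ceiling could contribute to an early stop. The missing points cannot be recovered after data collection.

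**Working it through.** **1. The plan's own figure.** Inputs from section 14: margin 2, SD 3, n = 34 per group, true difference 0.

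- SE = 3 × √(2/34) = 0.728.
- Normal power with each one-sided test at 0.05: 2Φ(2/0.728 − 1.645) − 1 = 0.730. The t version gives 0.718.
- Sample size for 70% power: 2 × [3 × (1.645 + 1.036)/2]² = 32.3, so 33; the t version gives 34.

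The stated size reproduces. It does so only with each test at one-sided 0.05; at 0.025 the power is 0.55 to 0.57. The wording "the study is powered to achieve 70% power with two-sided alpha = 0.05" should be clarified, but that is a side matter here.

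**2. Where the mid-thigh injection lies.** The documents give no thigh length. Assume a distance L from iliac spine to upper patella.

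- For L = 30 to 50 cm the midpoint L/2 is 15 to 25 cm above the upper patella, which is 0 to 10 cm above a 15-cm mark measured from there.
- The grid starts lower. With L = 36 to 50 cm and a joint line assumed 4 to 7 cm below the upper patellar margin, the midpoint is 36/2 + 4 = 22 to 50/2 + 7 = 32 cm above the joint line, or 7 to 17 cm above the top row.

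The injection is probably above the grid. By how much is an assumption, and it does not show how high the skin is numb.

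**3. If the cap hides a share of a true difference.** SD is held at 3, n = 34, margin 2, each test at 0.05 (t version). The observed difference is the true difference × (1 − share hidden).

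| True difference | 0 hidden | 25% | 50% | 75% |
|---|---|---|---|---|
| 3 points | 0.001 | 0.024 | 0.17 | 0.50 |
| 4 points | <0.001 | 0.001 | 0.05 | 0.38 |

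Entries are the chance of declaring equivalence. The share hidden is posited, not derived from the documents.

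**4. Block height simulated, few columns affected.** Assume the upper edge of numbness is normal with mean μ and SD 5 cm, and is the same in all c affected columns. The expected grid count is c × [Φ(μ/5) + Φ((μ−5)/5) + Φ((μ−10)/5) + Φ((μ−15)/5)]. The uncapped difference is c × (gap in cm)/5. For 13 against 22 cm and c = 2:

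- grid: 2 × (3.911 − 3.011) = 1.80;
- uncapped: 2 × 9/5 = 3.6;
- grid SDs: 1.79 (distal) and 0.63 (mid-thigh), against roughly 2 × 5/5 = 2 uncapped.

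| Mean edge, distal vs mid-thigh (cm) | Columns | Uncapped difference | Grid difference | P(equivalence) on grid |
|---|---|---|---|---|
| 13 vs 22 | 2 | 3.6 | 1.8 | 0.16 |
| 13 vs 22 | 3 | 5.4 | 2.7 | 0.002 |
| 13 vs 22 | 5 | 9.0 | 4.5 | about 0 |
| 14 vs 22 | 2 | 3.2 | 1.5 | 0.51 |
| 15 vs 22 | 2 | 2.8 | 1.2 | 0.85 |
| 13 vs 18 | 2 | 2.0 | 1.3 | 0.59 |
| 10 vs 19 | 2 | 3.6 | 2.5 | 0.002 |
| 10 vs 22 | 2 | 4.8 | 2.9 | about 0 |

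Uncapped, the chance is about 0.001 or less in every row except 13 vs 18. There the true difference equals the margin and the chance is the nominal 0.05.

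**5. Block height simulated, all five columns affected.** Edge SD 4 cm, arms 4 cm apart.

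| Mean edges (cm) | Uncapped difference | Grid difference | P(equivalence) on grid |
|---|---|---|---|
| 6 vs 10 | 3.99 | 3.96 | about 0 |
| 9 vs 13 | 4.00 | 3.80 | about 0 |
| 12 vs 16 | 3.96 | 3.22 | about 0 |
| 16 vs 20 | 4.05 | 1.83 | 0.10 |

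Attenuation is negligible when both edges lie well inside the grid. It grows as they approach or pass the top row.

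**The case against.** A reader might infer that the grid stops well below the mid-thigh injection, that the skin between is numb in that arm only, and that the result is therefore pulled towards equivalence. The documents do not support this, for four reasons.

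- No thigh length or injection height is given, and on some assumed lengths the gap is small.
- Injection level is not the upper limit of numb skin. That depends on which cutaneous branches are reached, which section 1 calls unclear. Section 1 also describes the block as used at or below the knee, and section 4 says the grid was placed on purpose to bracket the expected edge.
- The simulated rates are fragile. With the edges at 13 and 22 cm, going from two affected columns to three takes the rate from 0.16 to 0.002. Nothing in the documents fixes the number of columns, so no single rate describes this trial.
- It cannot be said that skin above 15 cm is never assessed. That is established for the primary count only, since the extent of the secondary mapping is not described.

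These points stand, and they make the bias conditional. They do not remove it. Placing the grid at the expected edge is an expectation that nothing in the plan checks. The primary data could not show how far numbness extends above a changed top point, and an undescribed mapping endpoint cannot be relied on to fill the gap. A bounded grid is a fair choice in a self-described pilot; a conclusion that reaches beyond it is not.

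**Conclusion.** The point holds in conditional form. It is certain from the documents that the primary count is capped at 15 cm, that the question carries no such limit, that a numb top row has no rule, and that a ceiling under TOST can only be harmless or favour equivalence when it hides part of a true difference. It is an assumption that the mid-thigh injection lies above the top row, and a further assumption that numbness reaches that far, more in one arm.

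The size is unknown. The illustrations run from no material effect, when the edge is inside the grid, to a false-equivalence rate of about 0.85, when both edges are at or above the top row and only two columns are affected. None of these is an estimate for this trial. The matter is worth fixing because the trial can cheaply collect the data that would settle it, and only while it is running.

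**What to change.** Keep the 20-point count as the primary outcome, with its 2-point margin and SD of 3. Then add to sections 3, 4 and 14:

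1. Report by arm the number of patients, and of columns, with a changed 15-cm point at each test time.
2. In any column whose 15-cm point is changed, continue cephalad in 5-cm steps up to one height fixed in advance and identical in both arms. Test the added points at baseline too. The stop should not be set by the skin wheal, because that would put a different ceiling in each arm.
3. Report the extended count by arm, with a confidence interval for the difference, as supportive. Do not carry the ±2 margin over as a formal test, since it was set for a 20-point count.
4. Word any equivalence conclusion as applying within 15 cm of the knee, unless top-row involvement is rare and similar in both arms.
5. State why 15 cm was chosen, and describe the method and extent of the secondary sensory mapping.

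The cost is under a minute of extra pinpricks in some patients, a few lines of protocol and a possibly narrower claim. The sample size does not change.

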Eligible and interested females of childbearing age will have a urine pregnancy test the morning of surgery. Exceptions include surgically sterile women or women with medically confirmed menopause. Urine (5 ml) will be collected for the urine pregnancy test (UPT). This is the routine clinical practice at Clements University Hospital, Zale Lipshy Hospital and the Outpatient Surgical Center as a part of the pre-procedure standard of care. Any females with a positive UPT will be excluded from the study.

Following the discussion and UPT (if necessary), informed written consent for clinical care and participation in the study will be obtained.

Once a patient is enrolled, they will be randomized to one of two groups, mid-thigh ACB or distal ACB, using a computer generated randomization program. The site will be marked, and a time out will be performed. A grid will be marked starting with anatomical landmarks at the knee joint: the medial inter-knee-joint point where the tibia meets the femur, the mid medial patella, the mid lateral patella, and along the same line at the semitendinosus tendon and 5cm posterior from that point. Then 5cm intervals will be plotted progressing cephalad to a total of 15 centimeters. This will yield 20 grid points.

The distribution of baseline sensation will be evaluated at the grid and documented. The degree of sensory block will be evaluated over the grid area with Neuropen prick testing on a scale of 0-1, with 1 = normal sharp sensation, 0 = change of sensation. The Neuropen will be used for the standardization of force.¹⁹⁻²¹ The primary outcome will be the number of grid-points with a change in sensation at 20 minutes and 30 minutes after the block. The second post block measurement is to ensure that the block is effective, as this will vary with each patient, and there is potential to miss important sensory change if measurement is taken too early. The current clinical guidelines list a block onset time between 15-30 minutes.

MVIC of the ipsilateral quadriceps muscle will be assessed using a handheld dynamometer and recorded.²²⁻²⁵

Patients will receive a preoperative ultrasound-guided single-injection ACB at either the mid-thigh or distal approach according to their randomization and according to the technique descriptions provided in the Background section of this protocol and consistent with standard UTSW peripheral nerve block procedures.

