- The adductor canal block will be performed using a linear HFL38xp or a linear HFL38x ultrasound probe (X-Porte or M-Turbo; SonoSite; Bothell, Washington). The site that is to receive the ACB will be sterilized with chlorhexidine gluconate 2% and 70% isopropyl alcohol prep. A skin wheal of lidocaine 1% (2-5mL) will be delivered. A Tuohy needle (17 gauges) will be inserted through the skin wheal under ultrasound guidance towards the target nerve location. Ropivacaine 0.5% 15ml will be injected for either adductor canal locations.²⁷
- The research intervention of this study will take place within the standard clinical context. The patient will receive an ACB regardless of their participation in this research in accordance with their anesthetic plan and their desires.
- **Follow-up visit:**
- A follow-up visit will be performed in person for inpatients or via phone for outpatients within 24 hours from discharge to assess for pain control, and monitoring side effects. It will take 10 minutes.
- **Monitoring Adverse Events**
- Adverse events will be monitored during the 24-h study period.

5. Sub-Study Procedures:

N/A

6. Criteria for Inclusion of Subjects:

1. Adult patients age \geq 18 years
2. Individuals undergoing surgery of the medial foot, medial ankle, medial leg or knee for which the anesthetic plan includes an adductor canal nerve block

Selection for inclusion will not be based on gender, race, or socioeconomic status. The study population of interest includes men and women of all races and socioeconomic status. There will be no participants from vulnerable populations, such as pregnant women, children or prisoners.

Patients can decline enrollment. If they do so, they will still receive a peripheral nerve block for postoperative analgesia according to the plan determined by the anesthesia provider at the time of service in accordance with the patient's wishes.

7. Criteria for Exclusion of Subjects:

1. Any known deficit of the ipsilateral lumbar nerve roots, ipsilateral lumbar plexus, ipsilateral femoral nerve, obturator nerve or saphenous nerve including diabetic peripheral neuropathy
2. Any local disorder of the skin or otherwise where blockade is to be performed
3. Body mass index >50
4. ASA classification greater than 3
5. Allergy to amide local anesthetic medications
6. Pregnancy
7. Incarceration
8. Inability to understand study procedures including inability to understand the English language

8. Sources of Research Material:

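### The distal-arm lidocaine wheal may fall at or near the upper rows of the sensory grid and the mid-thigh wheal above it, so skin numbness could count as block effect in the distal arm only

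*Combined protocol and SAP*

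**What the plan says.** Section 4 (Adductor Canal Blockade) gives one instruction for both arms: "A skin wheal of lidocaine 1% (2-5mL) will be delivered". It continues: "A Tuohy needle (17 gauges) will be inserted through the skin wheal under ultrasound guidance towards the target nerve location". The wheal therefore sits wherever the block needle enters.

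Section 3 has both blocks done "according to the technique descriptions provided in the Background section of this protocol". Section 2 (Background) then sets the two levels:

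- **Distal block:** "The transducer was initially placed on the medial aspect of the distal third of the thigh". The probe is next moved caudally to the adductor hiatus, and "the block location was selected 2 to 3 cm proximally to this area, in the distal adductor canal".
- **Mid-thigh block:** "The midpoint between the anterior superior iliac spine and the cephalad margin of the patella was measured", and the block is done at that midpoint.

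The grid (Sections 3 and 4) starts at knee-joint landmarks, from the lateral patella round the medial side to 5 cm behind the semitendinosus tendon. It then goes up the thigh: "Then 5cm intervals will be plotted progressing cephalad to a total of 15 centimeters". That is five columns by four rows, 20 points.

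Each point is scored "with 1 = normal sharp sensation, 0 = change of sensation". The primary outcome is the number of changed points at 20 and 30 minutes. Baseline is mapped before the block.

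**The concern.** Pinprick cannot tell skin numbed by infiltration from skin numbed by the nerve block. The pre-block baseline does not help, because the wheal is raised after it. If one arm's wheal lies among the grid points and the other's does not, the count can be inflated in one arm only. No text places the puncture on the grid map, flags nearby points or plans a sensitivity analysis.

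The direction would be fixed: more changed points in the distal arm. With no real difference, this lowers the chance of showing equivalence. With a real distal deficit, it hides part of that deficit and raises the chance of a false equivalence claim. The margin is only 2 points and planned power only 70%, so a fraction of a point can matter.

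**Working it through.** **1. The plan's own figure.** Section 14 gives a margin of 2, SD 3, n = 34 per arm and 70% power. The standard error is 3 × √(2/34) = 0.728. TOST power with true difference 0, each one-sided test at 0.05, t-based and integrated over the pooled SD, is 71.8% (normal approximation 73.0%). The smallest n reaching 70% is 34, so the plan's figure reproduces. With each side at 0.025, power would be 54.6%; the figures below use 0.05 per side.

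**2. Where the wheals lie.** The iliac spine-to-patella length L is not given; assume 36–50 cm. The grid top is 15 cm above the knee landmarks. Taking off about 2 cm for half the patella (assumed) puts it about 13 cm above the upper patella.

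| L (cm) | Distal third ends, L/3 (cm above patella) | Share of distal third within grid height, 13 ÷ (L/3) | Mid-thigh, L/2 (cm above patella) | Mid-thigh above grid top, L/2 − 13 (cm) |
|---|---|---|---|---|
| 36 | 12 | 100% | 18 | 5 |
| 45 | 15 | 87% | 22.5 | 9.5 |
| 50 | 16.7 | 78% | 25 | 12 |

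The mid-thigh wheal is clear of the grid throughout. The distal wheal is at grid level over most of the range if the puncture is in the distal third, but in a longer thigh it may be at or just above the top row.

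**3. How many points a wheal could cover.** Assume a numb disc of radius r that is still numb at 20–30 minutes. As a plausibility check, 2–5 mL spread 2.5 mm thick (assumed) gives r = √(V/(0.25π)) = 1.6–2.5 cm. Take r = 1–2.5 cm.

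- Spacing 5 cm both ways, disc wholly inside the grid: πr²/25 = 0.13 (r = 1), 0.28 (1.5), 0.50 (2), 0.79 (2.5).
- The text gives 5 cm for the rows and the last column only. With columns 8–10 cm apart (assumed), the range is π(1)²/50 = 0.06 to π(2.5)²/40 = 0.49.
- Points already numbed by the block add nothing. If half are (assumed), 0.13–0.79 becomes about 0.06–0.39.
- A disc centred on the top row loses about half its area; one well above it adds 0.

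**4. Effect on the design.** Step 1 rerun with the artefact as a shift between arms, true difference 0:

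| Artefact (points) | TOST power |
|---|---|
| 0 | 71.8% |
| 0.06 | 71.6% |
| 0.13 | 71.0% |
| 0.39 | 65.3% |
| 0.5 | 61.4% |
| 0.8 | 48.0% |

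If the artefact offsets a true 2-point distal deficit, the observed difference is 2 minus the artefact. False equivalence rises from 5% to 16.6% at 0.5 points (observed difference 1.5). A two-sided 5% test of difference, with none present, rejects 5.4% of the time at 0.13 points and 10.4% at 0.5.

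**The case against.** The strongest objection is location. The final distal site is defined only relative to the adductor hiatus, with no distance from the knee; the distal third is where scanning begins. Section 1 describes the tunnel receiving the local anesthetic as lying in the middle third of the thigh. On the assumed lengths, that third begins 12–17 cm above the patella, near or above the grid top. The distal description also gives no needle-entry side, so no grid column can be assigned. All of this stands. A reader might infer that the protocol's landmarks put the distal wheal inside the grid; they do not settle it.

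The second objection is size. The 0.13–0.79 range rests on 5 cm spacing in every column, a disc wholly inside the grid and no overlap with the block. Each assumption pushes the figure up. This stands too, which is why 0.8 is treated as a bound.

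Third, the trial calls itself a pilot and records sensory mapping, so an isolated numb point might be seen afterwards. That helps only in part: without a recorded puncture site, such a point cannot be attributed to the wheal.

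The objections do not remove the possibility of a one-arm artefact, or the lack of any means of detecting it.

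**Conclusion.** The concern holds as a possible one-arm measurement artefact in the primary outcome, of uncertain and probably modest size. The mean artefact is probably 0 to about 0.4 points, with equivalence power between 71.8% and about 65%; 0.8 points (48%) is an upper bound. This rests on an assumed L of 36–50 cm, a numb radius of 1–2.5 cm, numbness lasting to 20–30 minutes, the column spacing, and the share of nearby points already blocked. None of these is in the documents.

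A reader might go further and conclude that the primary comparison is biased toward the distal arm. The documents do not support that: the artefact is zero if the distal puncture lies clear of the grid, if the wheal has worn off, or if the nearby points are numb from the block anyway. What they do support is that, as planned, nobody could tell afterwards which of these applied.

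**What to change.** - Mark the puncture site on every patient's grid map, in both arms. The wheal and the block technique need not change.
- Keep the 20-point count as the primary outcome.
- Pre-specify one sensitivity TOST that drops the same grid positions in both arms: those within a fixed distance, for example 3 cm, of the distal-arm puncture sites. Settle the list from the puncture marks, before sensory results are compared by arm. State the margin to be used on the shortened count, and report whether the conclusion changes.
- Do not recode nearby points as unchanged, or rescale counts, in one arm only. On a 5 cm grid a 3 cm radius covers π(3)²/25 = 1.13 points, more than the largest artefact considered. Erasing genuine block effect of that size in the distal arm would shift the comparison the other way and cut power to about 32%.

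The cost is one mark on the data form, one extra analysis, and slightly less precision in that analysis because it uses fewer points.
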